1 PROTOCOL SUMMARY

1.1 Synopsis

Title	RESCUE: A Randomized, Blinded, Placebo-controlled, Parallel Group Design to Determine the Safety of RNS60 in Large Vessel Occlusion Stroke Patients Undergoing Endovascular Thrombectomy.
Protocol Number	06.5.1.H1
Trial Design	This study is a Phase 2, randomized, blinded assessor, placebo-controlled, parallel group, and two-dose design. Patients with a large vessel occlusion and acute ischemic stroke (AIS) who meet the criteria for endovascular revascularization will be given a 48-h infusion of either 0.5 mL/kg/h RNS60 (up to a maximum of 65 mL/h), 1 mL/kg/h RNS60 (up to a maximum of 130 mL/h), or 1 mL/kg/h (up to a maximum of 130 mL/h) placebo (normal saline) starting within 30 minutes of randomization (but prior to arterial access closure) with the exact time to start dosing being determined by the timing of the informed consent. Randomization will be done with block urn randomization to balance age, National Institutes of Health Stroke Scale (NIHSS), and Alberta stroke programme early CT score (ASPECTS). Outcomes will be evaluated throughout a 90-day observation period. Block urn randomization provides consistent imbalance control but provides greater allocation randomness compared with permuted block design and can be used for more than three arms (see Section 6.3.1). Block urn designs have been used in other stroke trials.
Trial Objectives	
The primary objective is to determine the safety of the neuroprotectant RNS60 in patients with large vessel occlusion (LVO) AIS receiving a 48-h infusion of either 0.5 mL/kg/h RNS60 (up to a maximum of 65 mL/h) or 1 mL/kg/h RNS60 (up to a maximum of 130 mL/h).
 
The secondary objectives are to evaluate the efficacy of RNS60 in:
 
 1) Reducing global disability 2) Reducing mortality rate 3) Improving neurological outcome 4) Reducing worsening of stroke* 5) Reducing functional dependence 
* Worsening of stroke is defined as progression, or hemorrhagic transformation of the index stroke, as documented by brain imaging, and that is (a) life-threatening requiring intervention and/or (b) results in increased disability as gauged by a \geq 4-point increase from lowest NIHSS pre decline and/or (c) results in death.

	
The tertiary objectives are to evaluate the efficacy of RNS60 in:
 
 • Decreasing infarct volume • Improving health related quality of life
Safety Outcomes	
Safety outcomes include:
 
 • Serious adverse events (SAEs) to Day 90 • 90-day mortality 
Additional Safety outcomes include:
 
 • Adverse events (AEs) to Day 90 • Drug administration discontinuations due to AEs • Baseline and 48-h vital signs • Baseline and 48-h electrocardiogram • Baseline and 48-h chest X-ray (CXR)
Efficacy Outcomes	
The efficacy outcomes (secondary) are:
 
 1) Mean modified Rankin Scale (mRS) at Day 90 2) 90-day mortality 3) Mean NIHSS at 24h and Day 90 4) Proportion of patients exhibiting a worsening of their index stroke.* 5) Mean Barthel Index (BI) at Day 90 relative to pre-stroke BI. 
*Worsening of stroke is defined as progression, or hemorrhagic transformation of the index stroke, as documented by brain imaging, and that is (a) life-threatening requiring intervention and/or (b) results in increased disability as gauged by a \geq 4-point increase from lowest NIHSS score pre decline and/or (c) results in death.
 
Tertiary/exploratory outcomes include:
 
 1) Infarct progression/regression as measured by MRI brain imaging. 2) Health-related quality of life, as measured by the 5-level EuroQoL 5D index (EQ-5D-5L) at Day 90.

Number of Participants	
An initial target of 100 male and female participants with LVO AIS and who are selected for endovascular revascularization will be enrolled.
 
Attrition factors include death from stroke but not treatment (10%), symptoms of fluid overload (20%) and early discharge (5%).

Inclusion/Exclusion Criteria	
Inclusion Criteria
 
 1) AIS patients selected for emergency endovascular treatment. 2) Age 18 years or older. 3) Stroke symptom onset or, if not known, last known well time to randomization within 24 hours. 4) Disabling stroke defined as a baseline NIHSS score: 
 a. NIHSS score NIHSS > 5 for internal carotid artery (ICA) and M1-middle cerebral artery (MCA) occlusion or b. NIHSS > 10 for M2-MCA occlusion. 5) Confirmed symptomatic intracranial occlusion at one or more of the following locations: Intracranial carotid I/T/L, M1 or M2 segment MCA. Tandem extracranial carotid and intracranial occlusions are permitted. 6) Pre-stroke (24 hours prior to stroke onset) historical modified Rankin Scale (mRS) ≤ 2. Patient must be living independently without requiring nursing care. 7) Qualifying imaging performed less than 2 hours prior to randomization. 8) Consent process completed as per applicable laws and regulation and the IRB requirements. 
Exclusion Criteria
 
 1) Evidence of a large core of established infarction defined as ASPECTS 0-4. 2) Evidence of absence of collateral circulation on qualifying imaging (Collateral score of 0 or 1 if mCTA is used, or absence of adequate ischemic penumbra in the judgment of the Investigator if CTP is used). 3) Any evidence of intracranial hemorrhage or mass lesion on the qualifying imaging. 4) Planned use of an endovascular device not having approval or clearance or has been recalled by the relevant regulatory authority.

	
5) Endovascular thrombectomy procedure is completed as defined by the presence of arterial access closure.
 
6) Clinical history, past imaging or clinical judgment suggesting that the intracranial occlusion is chronic or there is suspected intracranial dissection such that there is a predicted lack of success with endovascular intervention.
 
7) Estimated or known weight > 130 kg (287 lbs).
 
8) Known pregnant/lactating female.
 
9) Myocardial infarction within 6 months prior to Screening including non-Q wave MI; Diagnosis of congestive heart failure (CHF) with either:
 
 a) current clinical signs and symptoms of ventricular dysfunction (e.g., edema, shortness of breath), b) CHF medication adjustment within the prior 30 days or c) ejection fraction (if report available) of 30% or less measured in the 6 months prior to Screening; 
as either medically documented or reported by patient or another person considered by the Investigator to be reasonably reliable.
 
10) Known renal impairment defined as requiring renal replacement therapy (hemo- or peritoneal dialysis)
 
11) Inability to have MRI imaging (Non- MR compatible implants or any other foreseeable reason (including claustrophobia)
 
12) Severe or fatal comorbid illness that will prevent improvement or follow up.
 
13) Inability to complete follow-up treatment to Day 90.
 
14) Participation in another clinical trial investigating a drug, medical device, or a medical procedure in the 30 days preceding trial inclusion and throughout the duration of the trial.
 
15) Reported known seizure at time of stroke onset.
 
16) Ischemic stroke within previous 30 days.
 
17) Patients in normal sinus rhythm with a known QTcF > 460 ms at Screening.
 
18) Any other symptom that in the investigator's opinion may complicate or preclude the subject from participating in this trial.

Treatment	RNS60 0.5 mL/kg/h (up to a maximum of 65 mL/h) or RNS60 1 mL/kg/h RNS60 (up to a maximum of 130 mL/h) intravenous infusion.

Consent	
Initial Informed Consent Participants or their legally authorized representative will be required to sign a statement of informed consent that meets the requirements of applicable laws and regulation and Internal Review Boards (IRBs).
 
Regained Capacity Consent If the original consent process involved anyone other than the participant, and if required by local standards, consent will be sought for the remaining procedures from the participant once they are deemed to have regained capacity.
 
Note: Electronic consent tools may be used for initial and regained capacity consent, as permitted under applicable laws and regulations and the applicable IRB Committee.

Randomization Method	Treatment will be assigned using 1:1:1 randomization of RNS60 0.5 mL/kg/h: RNS60 1 mL/kg/h: placebo (normal saline) with block urn randomization by age, NIHSS score, and ASPECTS score (8 urns).
Duration of Treatment	Participants will receive a 48-h infusion of study drug or placebo. Each participant will be followed for 90 days. At Day 30 and Day 90 it is preferred that participants will return to clinic. If an in-clinic visit is not possible, the participant (or LAR) will be contacted by telemedicine (preferred) or by telephone (last option).
Laboratory Tests	If the participant is female and is of childbearing potential, a pregnancy test (urine or serum point-of-care pregnancy test) must be completed. In order to support the assessment of safety, pre-dose (baseline) and post-dose (48-h) complete blood count, electrolytes including magnesium, liver function test panel (LFT), blood urea nitrogen (BUN), creatinine, chest Xray (CXR) and cardiac electrocardiogram (at baseline, 24-h and 48-h) results will be reported and analysed.
Assessment of Efficacy	As the primary purpose of this trial is the assessment of safety, there is no power analysis for efficacy. However, the design and analyses of this trial will provide estimates for the powering of a subsequent trial for efficacy. The primary efficacy metric for assessment of efficacy is a lower mean mRS at 90 days.
Statistical Assumptions	Analyses will be examined on the intent-to-treat (ITT) sample, defined as all randomized participants, regardless of treatment actually received. The per protocol sample will also be examined separately. Patients who receive treatment but do not get full 48 hours of treatment due to fluid overload or early discharge will be included in the ITT analysis. Patients who complete the full 48 hours will be included in both per protocol and ITT analysis.

	
All analyses will be accomplished using SAS Software 9.4 (SAS Inc. Cary, NC). Primary: The frequency of SAEs, SAEs resulting in death, AEs, and discontinuations due to AEs will be summarized as counts and percentages between the three arms. Comparisons will be conducted using Fisher's Exact tests.
 
Secondary: Comparisons between conditions for mRS will be evaluated using generalized mixed modeling assuming a binomial distribution (0-6) with sandwich estimation nested by site and patient, when applicable. Pairwise comparisons of mRS will be conducted at Day 90 using a Dunnett correction. In addition, simple and interaction effects between pre-stroke, discharge, 30-day and 90-day mRS by condition will be examined. Both NIHSS and BI at Day 90 will be examined in a similar fashion assuming a binomial distribution (0-42 & 0-100) with sandwich estimation. Pairwise comparisons between conditions will be conducted at Day 90 using a Dunnett correction. In addition, simple and interaction effects between pre-treatment, discharge, 30-day and 90-day NIHSS and BI by condition will be examined. Mortality will be examined using Kaplan-Meier estimation with pairwise comparisons with a Dunnett correction. DWI volume post treatment and at 48 hours, and 90-day T2 will be modeled between conditions using generalized linear modeling assuming a normal or lognormal distribution (where appropriate), where simple and interaction effects will be examined. Because superiority over placebo and lower dose is hypothesized, testing will reflect this superiority framework. Because the main aim of this trial is to examine safety, efficacy analysis results are intended to yield estimates to inform powering for a future efficacy trial. Alpha is established at the 0.05 level and all interval estimates will be calculated for 95% confidence.

Data Safety Monitoring Board	A Data Safety Monitoring Board (DSMB) will monitor patient safety and scientific integrity during the trial.

Table 1-1: Schedule of Activities for Randomized Participants

Visit/Contact	V1	V2	V3	V4	V5	V6/ End of Trial
Day	Day 0 Baseline	Day 1 Post-EVT	Day 2/or early discharge	Day 6 ¹ or discharge	Day 30 ²	Day 90 ²
Window		(24 h+/-4h)	(48 h+4h)		(±5 d)	(-21 to +7d)
Informed consent	X					
Regained capacity informed consent ³			X	X	X	X
History and physical examination ⁴	X	X	X			
Weight ⁵	X		X			
Vital Signs (BP, HR, Temperature) ⁶	X	X	X			
Chest radiograph	X ¹²	X	X			
Electrocardiogram ⁷	X ¹²	X	X			
Randomization/ Study drug administration	X	X	X			
Continuous telemetry ⁷	X	X	X			
Mortality		X	X	X	X	X
NIHSS ¹³	X	X	X	X	X	X
mRS	X			X	X	X
Barthel Index	X				X	X
EQ-5D-5L						X
Imaging (NCCT & mCTA)	X					
Endovascular Procedure	X					
MRI head ⁸		X	X			X
Laboratory Assessments	X ⁹		X			
Pregnancy test ¹⁰	X					
Blood collection for RNA analysis ¹¹		X	X			X
Blood collection for Plasma Biomarker		X	X			X
AE				Collected to Day 90		
SAE				Collected to Day 90		
Prior medications	X					
Concomitant medications				Collected to Day 90		

1. Visit will occur at Day 6 or hospital discharge if prior to Day 6.
2. At Day 30 and Day 90 it is preferred that participants will return to clinic. If an in-clinic visit is not possible the participant can be contacted by telemedicine (preferred) or by telephone (last option).
3. If the original process involved anyone other than the participant (and if required), site staff will make ongoing efforts until: (1) regained capacity consent is obtained from participant, (2) death, or (3) completion of the Day 90 assessment.
4. Physical exam every 8-12 hours during Day 1 and Day 2.
5. At baseline estimated or actual weight will be collected. If an estimated weight was collected at baseline, actual weight should be collected as soon as feasible and prior to discharge.
6. Vital signs (BP, HR only) will be recorded immediately before and after completion of the study drug infusion, and every 8-12 hours during Day 1 and Day 2, temperature will be collected at baseline only if standard of care.
7. Abnormal electrocardiogram or continuous telemetry result that suggests clinical instability will prompt a formal cardiology consult.
8. MRI head with perfusion imaging within approximately 2h post-EVT on Day 1 and at 48h +/- 4h. MRI head only at 90d.
9. Blood should be drawn at baseline, but results are not required prior to randomization. Results from primary hospital (within 8 hours) are accepted.
10. If the participant is female and is of childbearing potential a pregnancy test (urine or serum point-of-care pregnancy test) must be collected at baseline, but result is not required prior to randomization.
11. Day 1 collection 12-24 h (+/-4 hours) after additional consent is obtained for optional collection.
12. Results from the baseline ECG and CXR are not required prior to randomization.
13. NIHSS score is obtainable in-person or via telemedicine visit only (not over the phone).

d = days; h = hours

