3.2 Outcomes

3.2.1 Primary Safety Outcomes

- 1) The safety outcomes are the frequencies and severities of SAEs and 90-day mortality

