10.2.2 Imaging

At baseline all participants will undergo NCCT and CTA (with mCTA preferred) imaging for assessment of inclusion into the trial. If mCTA is not standard of care at the imaging facility, single phase CTA (CTA) can be used to confirm intracranial occlusion eligibility. If CTA is not available, CTP may be used. To evaluate for the presence or absence of collaterals, mCTA, single phase CTA or CTP can be utilized. The immediate post-thrombectomy (within approximately 2 hours) and 48-h MRI will be used to assess perfusion imaging and infarct volume and will include a minimum of axial DWI, gradient-echo (GRE), FLAIR, T2, and 3D T1 weighted dataset). The 48-h MR is considered a standard of care imaging procedure. If any MRI cannot be obtained (due to subject compliance or limitations) a CT will be performed.

The baseline NCCT and CTA and all brain/neurovascular imaging conducted up to the Day 90 MR will be rendered anonymous and sent to the central core imaging lab. The core imaging lab staff will review the imaging as per an Imaging Charter in order to ensure adherence to the imaging guidelines and enrollment criteria for training purposes. The core imaging lab will confirm determination of baseline ASPECT scores, as well as reperfusion rates (TICI scores) and infarct growth from immediately after thrombectomy to 48h. In addition, overall injury to the

affected hemisphere will be compared between groups by comparing volume loss/gliosis between the 90-d and post-thrombectomy MRI.

For all interval times assessed from imaging, the time zero will be the first slice of the NCCT scan. Imaging date and time will be collected in the CRF.

Notes:

The use of a dynamic CTA or multiphase CTA data acquisition protocol is preferred. Baseline NCCT and CTA may be completed at a hospital affiliated with the trial site.

10.3 Appendix 4: Adverse Events: Definitions and Procedures for Recording, Evaluating, Follow-up, and Reporting

AE Definition

An AE is any untoward medical occurrence in a patient or clinical investigation participant administered a pharmaceutical product and which does not necessarily have to have a causal relationship with this treatment.
 
An AE can therefore be any unfavorable and unintended sign (including an abnormal laboratory finding, for example), symptom or disease temporally associated with the use of a medicinal product, whether or not considered related to the medicinal product.

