
Adverse Drug Reaction (ADR)
 
In the pre-approval clinical experience with a new medicinal product or its new usages, particularly as the therapeutic dose(s) may not be established: all noxious and unintended responses to a medicinal product related to any dose should be considered adverse drug reactions. The phrase "responses to a medicinal product" means that a causal relationship between a medicinal product and an adverse event is at least a reasonable possibility, i.e., the relationship cannot be ruled out.

Unexpected Adverse Drug Reaction
 
An adverse reaction, the nature or severity of which is not consistent with the applicable product information (e.g., Investigator's Brochure for an unapproved investigational medicinal product).

Events Meeting the AE Definition

• A new illness• The worsening of a concomitant illness• Any abnormal laboratory test results (hematology, clinical chemistry, or urinalysis) or other safety assessments (e.g., ECG, radiological scans, vital signs measurements), including those that worsen from baseline, considered clinically significant in the medical and scientific judgment of the investigator (i.e., not related to progression of underlying disease).• Exacerbation of a chronic or intermittent pre-existing condition including either an increase in frequency and/or intensity of the condition.• New conditions detected or diagnosed after study intervention administration even though it may have been present before the start of the study.• Signs, symptoms, or the clinical sequelae of a suspected drug-drug interaction.• Signs, symptoms, or the clinical sequelae of a suspected overdose of either study intervention or a concomitant medication. Overdose per se will not be reported as an AE/SAE unless it is an intentional overdose taken with possible suicidal/self-harming intent. Such overdoses should be reported regardless of sequelae.
Events NOT Meeting the AE Definition

- Any clinically significant abnormal laboratory findings or other abnormal safety assessments which are associated with the underlying disease.
- The disease/disorder being studied or expected progression, signs, or symptoms of the disease/disorder being studied, unless more severe than expected for the participant's condition.
- Medical or surgical procedure (e.g., endoscopy, appendectomy): the condition that leads to the procedure is the AE.

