Worsening of stroke is defined as progression, or hemorrhagic transformation of the index stroke, as documented by brain imaging, which is (a) life-threatening requiring intervention and/or (b) results in increased disability as gauged by a ≥ 4-point increase from lowest National Institutes of Health Stroke Scale (NIHSS) pre decline and/or (c) results in death.

5) Barthel Index at Day 90.

The BI is an index of functional independence. Its values range from 0 to 100, with higher scores indicating greater independence.

Table 4. Scales and score range in BI

| Item | Score range |
|-----------------------------------|-------------|
| Feeding | 0-10 |
| Bathing | 0-5 |
| Grooming | 0-5 |
| Dressing | 0-10 |
| Bowels | 0-10 |
| Bladder | 0-10 |
| Toilet use | 0-10 |
| Transfers (bed to chair and back) | 0-15 |
| Mobility (on level surfaces) | 0-15 |
| Stairs | 0-10 |

Item scores vary in increments of 5 points.

6) Health-related quality of life, as measured by the EuroQol health-related quality of life (EQ-5D-5L) at Day 90.

EQ-5D-5L is developed by EuroQol Research Foundation and is a generic instrument for measuring and describing health-related quality of life.

It consists of two elements, a 5-item questionnaire and an EQ-Visual Analogue Scale (VAS). Both elements are interviewer administered by study staff.

EQ-5D-5L is a version that further improves the sensitivity of EQ-5D-3L, provides respondents with a wider range of options to describe their health and is comprised of five response levels to five different dimensions.

- **5-Item Questionnaire:** The questionnaire provides a simple descriptive profile of health state. The questionnaire comprises 5 dimensions (mobility, self-care, usual activities, pain/discomfort, anxiety/depression) and each dimension has 5 response levels (1-no problems, 2-slight problems, 3-moderate problems, 4-severe problems,

5-unable to/extreme problems). The resulting 5-digit code corresponds to the response of each dimension of the health state. For instance, 11111 and 55555 indicate the best health condition and the worst health condition, respectively.

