Additionally, neurological functioning at Day 90 will be examined by NIHSS scores at Day 90 between the three treatments (RNS60 1.0 mL/kg/h, RNS60 0.5 mL/kg/h, and placebo 1.0 mL/kg/h). GLM analysis and missing data imputation analysis at Day 90 will be performed using the same approach described above for neurological functioning using 24-hour NIHSS scores.

4. The proportion of subjects with worsening of stroke over the 48-hours/duration of admission:

Worsening of stroke is defined (i.e., Yes or No) as: progression, or hemorrhagic transformation, of the index stroke as documented by medical imaging and that is (a) life-threatening requiring intervention and/or (b) results in increased disability as gauged by a \geq 4-point increase from lowest NIHSS pre decline and/or (c) results in death. Subjects with worsening of stroke will be identified based on a \geq 4-point increase in their worst minus best NIHSS score and adverse events status (life threatening requiring intervention or death) as collected in the CRFs.

The simple effect of treatment on worsening stroke at 48 hours/admission duration will be examined by comparing the proportion of subjects who had worsening stroke (Yes or No) between the three treatments (RNS60 1.0 mL/kg/h, RNS60 0.5 mL/kg/h, and placebo 1.0 mL/kg/h) using GLM using residual pseudo-likelihood with a subject-specific expansion (RSPL) assuming a binary distribution. Covariates include the Age, baseline NIHSS, and baseline ASPECTS as binary factors used for block urn randomization, log of baseline infarct volume, baseline perfusion status, baseline occlusion location, and study site.

The predicted probability for each treatment group and LS mean difference between high-dose and placebo and low-dose and placebo groups along with the 95% CIs will be provided using the LSMEANS/DIFF statement. The comparison of the two combined active arms versus placebo will be performed using the LSMESTIMATE statement with the ILINK option. The odds ratio will also be calculated. The P-value for the hypothesis testing will also be provided. Treatment difference will be assessed with a 2-sided alpha level of 0.05.

The sample SAS code planned for the analysis is outlined below.

5. Barthel Index.

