3.5.1 Adverse Events (AEs)

An AE is defined as any untoward medical occurrence in a subject or clinical investigation participant administered a pharmaceutical product and which does not necessarily have to have a causal relationship with this treatment.

An AE can therefore be any unfavorable and unintended sign (including an abnormal laboratory finding, for example), symptom or disease temporally associated with the use of a medicinal product, whether or not considered related to the medicinal product. AEs will be captured from the start of study drug infusion through study completion (Day 90). All AEs will be coded to system organ class and preferred term using MedDRA version 24.0. A medical review of the coding reports will be performed prior to database lock. Treatment-emergent adverse events (TEAEs) are defined as AEs that start after the study drug infusion.

The investigator will grade the intensity of the AE as mild, moderate, or severe.

The relationship of an AE to study drug will be assessed as related, possibly related, or unrelated.

An overview of AEs will be provided including counts and percentages of subjects (and event counts) with the following:

- Any TEAEs (overall and by maximum severity)
- Any study drug related TEAEs (overall and by maximum severity)
- Any SAEs
- Any treatment-emergent serious AEs (TESAEs)
- Any study drug related TESAEs
- Any TEAEs leading to discontinuation of study drug infusion
- Any AEs leading to death
- TEAE occurrence by Month (Day 0-Day 7, Day 8 – Day 14, Day 15 – Day 21, Day 22 – Day 30, Day 31-Day 60, and Day 61-Day 90)

Counts and percentages of subjects (and event counts) will also be presented by system organ class and preferred term for each of the categories in the overview. If more than one event occurs with the same preferred term for the same subject, the subject will be counted only once for that preferred term using the most severe occurrence for the summary by severity. The number of events will be presented for overall category of TEAE and for each system organ class and preferred term. The number of events will not be presented for each category of maximum severity. AE listings will include the following information:

- Subject ID
- Adverse event term
- Adverse event preferred term
- System Organ Class
- Start date
- Outcome
- End date
- Relationship to study drug
- Action taken with study drug

- Severity
- SAE Criteria

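### Hemorrhagic transformation is named as an outcome only inside the worsening-of-stroke efficacy composite, with no component reporting and no dependable AE route, so this safety trial has no prespecified, reliable by-arm bleeding result.

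*Protocol*

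**What the plan says.** The Protocol's primary aim is safety, and section 3.2.1 sets the headline measures: "The safety outcomes are the frequencies and severities of SAEs and 90-day mortality". The additional safety outcomes in the synopsis are AEs, discontinuations due to AEs, vital signs, ECG and chest X-ray. Bleeding is not on any safety list in the Protocol (synopsis, Table 3-1, 3.2.1, 9.3.2) or the SAP (2.3.1, 3.4.1, 3.5).

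Hemorrhagic transformation is named as an outcome in one place only, the worsening-of-stroke endpoint. The Protocol synopsis defines it under the efficacy outcomes: "Worsening of stroke is defined as progression, or hemorrhagic transformation of the index stroke, as documented by brain imaging". SAP 2.3.2 lists it as secondary efficacy endpoint 4: "Worsening of stroke is defined as progression, or hemorrhagic transformation of the index stroke, as documented by brain imaging, which is" life-threatening and requiring intervention, or disabling by the NIHSS rule, or fatal. SAP 3.4.2 (4) repeats the two pathways ("progression, or hemorrhagic transformation, of the index stroke as documented by medical imaging") and places the endpoint at ranks 4, 9 and 14 of the hierarchy. For the analysis, subjects are identified from a "4-point increase in their worst minus best NIHSS score and adverse events status", the latter meaning life-threatening events requiring intervention, or death.

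The AE route is separate. SAP 3.5 summarizes safety data by treatment actually received, and SAP 3.5.1 adds: "Counts and percentages of subjects (and event counts) will also be presented by system organ class and preferred term". Protocol Appendix 4 lists among events that are not AEs: "The disease/disorder being studied or expected progression, signs, or symptoms of the disease/disorder being studied", with an exception for events more severe than expected for that participant.

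**The concern.** The composite joins two events on which a neuroprotectant given around thrombectomy could act in different directions. Ischemic progression is what the drug is meant to reduce; bleeding into the infarct after reperfusion is a possible harm. In a single yes/no variable a rise in one can be offset by a fall in the other, and the planned output would not show it. The trial could report no difference, or an apparent benefit, on worsening of stroke while bleeding had increased. In a trial whose primary purpose is safety, the reader needs a bleeding comparison that does not depend on how each site reads the AE definition.

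**Working it through.** **Step 1. Can the composite be split afterwards?** The definition requires imaging documentation of progression or transformation. The identification rule in SAP 3.4.2 (4) uses NIHSS change and AE status, and has no flag for which pathway occurred. Protocol 10.2.2 says the post-thrombectomy and 48-hour MRI "will include a minimum of axial DWI, gradient-echo (GRE), FLAIR, T2", so a gradient-echo sequence is acquired. The core-lab readouts named there are ASPECTS, TICI, infarct growth and 90-day volume loss or gliosis; a hemorrhage reading is not named. As written, the split is not assured.

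**Step 2. Do the AE tables fill the gap?** Partly.
- A bleed recorded as an AE or SAE appears by arm under its preferred term (SAP 3.5, 3.5.1).
- Every death to Day 90 is an SAE, reported with its cause (Protocol 10.3.1).
- Appendix 4 excludes expected progression of the studied disease unless more severe than expected. It also excludes abnormal safety assessments associated with the underlying disease, with no severity exception. The same appendix counts radiological scans among safety assessments.
- Section 10.3.1 says an event that is not an AE cannot be an SAE even when a seriousness criterion is met.
- Neither document says whether transformation of the index infarct falls under these exclusions. Two sites could record the same non-fatal bleed differently.

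**Step 3. How large can the masking be?** The documents give no event rates and state that no power analysis was done, so there is no planned figure to reproduce. The only design input is 100 participants at 1:1:1, that is 100/3 = 33.3, taken as 33 per arm. The event counts below are assumed.

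| | High dose | Placebo |
|---|---|---|
| Hemorrhagic | 4 | 1 |
| Ischemic progression | 1 | 4 |
| Composite | 5/33 | 5/33 |

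Newcombe interval for d = p1 - p2, with Wilson limits (l, u) for each arm: lower = d - √[(p1 - l1)² + (u2 - p2)²]; upper = d + √[(u1 - p1)² + (p2 - l2)²].

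- Composite: p = 0.152 in both arms, Wilson limits 0.067 to 0.309. d = 0; half-width √(0.085² + 0.158²) = 0.179. Result: 0 points, 95% CI -18 to +18.
- Bleeding: p1 = 4/33 = 0.121 (0.048 to 0.273); p2 = 1/33 = 0.030 (0.005 to 0.153). d = 0.091. Lower = 0.091 - √(0.073² + 0.123²) = -0.052. Upper = 0.091 + √(0.152² + 0.025²) = 0.245. Result: +9 points, 95% CI -5 to +24.
- Odds ratio for bleeding: (4 × 32)/(1 × 29) = 4.4. Two-sided Fisher p = 0.36.

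Cancellation need not be exact. With assumed rates of progression/bleeding of 15%/5% on placebo and 5%/10% on high dose, the composite falls from 20% to 15%, which looks like benefit, while bleeding doubles.

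**Step 4. What could a separate bleeding table show?** At 33 per arm, 0/33 still has a two-sided exact 95% upper limit of 10.6%. Fisher p ≤ 0.05 needs splits such as 0 versus 6 or 1 versus 8. Over the assumed scenarios examined, with bleeding two to just over three times as frequent on high dose, Fisher power for bleeding alone ran from 2.5% to 17.7%.

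**The case against.** A reader might infer that bleeding is counted nowhere except in the composite, or that the trial will publish no bleeding data by arm. The documents do not support that: the AE and SAE tables are by preferred term and treatment received, and fatal bleeds are always SAEs.

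The case against goes further. The progression exclusion has its severity exception. Events meeting the worsening criteria are by definition life-threatening, disabling or fatal, so many would satisfy it. The endpoint definition names transformation alongside progression, which suggests the two are distinct, and Appendix 4 counts new conditions diagnosed after treatment as AEs. Life-threatening and fatal worsening reaches the composite through AE records, so those events should also be in the AE tables. The SAP, which governs, tests the composite two-sided, unlike the Protocol's one-tailed plan. The counts above are invented and symmetrical, and the only major risk the Protocol names is fluid overload. The Imaging Charter and the DSMB charter are not among the documents reviewed and may already provide a hemorrhage reading or review.

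Most of this stands, and it limits the point to dependability. It does not close the gap. Worsening that qualifies only through the NIHSS limb has no required AE record. The exclusion for disease-related abnormal findings has no severity exception. The classification of transformation is left to inference, and no component breakdown is planned.

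**Conclusion.** The point holds in this limited form. Hemorrhagic transformation is a named outcome only within an efficacy composite, its components are not reported separately, and its capture as an AE is left unsettled by Appendix 4. The trial therefore has no prespecified, dependable by-arm bleeding result, and opposite effects can cancel in the composite. The illustration (0 points on the composite against +9 points, 95% CI -5 to +24, on bleeding) shows that masking is possible. It rests on assumed counts and is not a forecast; the documents contain no evidence that the drug increases bleeding. Nor could a reader conclude that separate reporting would establish or exclude harm at this sample size: p = 0.36 in the illustration, and the power figures are low. The gain is a visible estimate with its uncertainty, which suits a trial that claims no power and is meant to inform a later one.

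**What to change.** Leave the composite and its ranks in the hierarchy unchanged, and make three additions.

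1. In SAP 3.5, add one Safety Population table by actual treatment giving patients with (i) hemorrhagic transformation and (ii) ischemic progression meeting the worsening criteria, with risk differences and 95% CIs against placebo, high dose first.
2. In Protocol Appendix 4, state that imaging-documented hemorrhagic transformation is always recorded as an AE, so that neither exclusion removes it.
3. Record the type of worsening in one CRF field. If the Imaging Charter already specifies a hemorrhage reading, cite it and use that reading instead.

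The cost is one table, one sentence and possibly one data field. No new scan is needed, because the endpoint definition already calls for imaging documentation and the gradient-echo sequence is already acquired. Sample size does not change. The downside is small counts per component and wide intervals, so the table should be labeled as estimation.
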